Over the past several years, there were studies suggesting that, compared to the traditionally high frequency stimulation of 130Hz, low frequency stimulation of 60Hz improves the FOG¹⁶⁻¹⁹ and dysarthria^{15, 19}. The beneficial effect was not necessarily only seen in chronically stimulated patients with disease progression, as it was also seen in patients with newly activated bilateral STN DBS¹⁹.

More recently, we for the first time further studied the effect of the 60Hz stimulation on another axial symptom, dysphagia, in patients on bilateral STN DBS who had medication refractory FOG at 130Hz²⁰ (supported by MJFF under Rapid Response Innovation Award program to TX). We found that 60Hz stimulation, compared to the traditional 130Hz, decreased not only the aspiration frequency by modified barium swallowing (MBS) test and swallowing difficulty by swallowing questionnaire, but also the medication refractory FOG (by SWS stand-walk-sit test and FOG questionnaire), and axial symptom subscore and general parkinsonism motor symptom UPDRS-III score²⁰. The beneficial effect of the 60Hz stimulation persisted during the 6-week study period, except that one of the patients had to switch back to 130Hz stimulation in 3 weeks due to worsening of the hand tremor.

The effect of the 60Hz stimulation on STN DBS patients without FOG at 130Hz stimulation was also studied, with significant improvement on axial and motor symptoms in 14 patients in an acute phase study²¹, and mild improvement on gait without improvement on other motor symptoms in another study²², suggesting the overall benefit of the 60Hz stimulation, though may not as great as seen in these with FOG at 130Hz stimulation.

However, it remains unknown whether the beneficial effect of the 60Hz stimulation would persist on extended chronic stimulation beyond the 6-week period, and whether there is carry-over effect during the study across different test conditions of 30-minute apart in our previous study²⁰. Clarifying these two questions is crucial for the clinical application of the 60Hz stimulation chronically and confidently to treat the medication refractory axial symptoms.

So far, there was only one study showing persistent benefit of the 60Hz stimulation on FOG in 85% of the 13 patients with bilateral STN DBS at medication off state following up in 8 months¹⁶. There were two other studies challenging the chronic benefit of the low frequency stimulation²³⁻²⁴. One of them reported an improvement in the gait immediately after switching the 130Hz stimulation to 80Hz at medication on state in 11 STN DBS patents, but the benefit only lasted for less than 1 month²³. The other one reported no benefit at 80Hz stimulation compared to 130Hz in axial symptoms following for almost 4 months (111.5 days on average) in 45 patients²⁴. Worth noting that none of these two studies was really studying FOG, as one of them had no FOG on exam and the other one was not assessing FOG. Besides, these two studies used 80Hz, instead 60Hz, stimulation. None of them studied swallowing function either.

According to our continuous observation since we published our study²⁰, all of our 5 out of 7 patients who was on 60Hz simulation for 6-week study period remains on 60Hz since then for

its benefit on axial symptoms including FOG, over the period of up to 14 months follow up so far, which indicates a sustained chronic benefits. The 2 of the 7 patients were not on 60Hz stimulation after the previous study because of slightly worsening of tremor in 1 of them, and skin infection after the battery replacement (unrelated to the study) in another one. A formal randomized double blind prospective cross-over study on the chronic benefit of the 60Hz stimulation over an extended period of at least 6 months, corrected for the potential carry-over effects on this crossover study (DBS off, 60Hz or 130Hz while all at medication on state) at the acute (visit 1) and chronic phase (visit 2), is needed to enhance the quality of the study, the evidence level and the level of the recommendation in clinical applications to treat the axial symptoms which are refractory to usual DBS setting and medications with high morbidity and mortality of the PD.

All Parkinson's disease patients who have had aspiration pneumonia within the past one month before the test will be excluded.

This study is basically an extension study of our previous one (IRB 13-0566; Effects of the stimulation frequency of STN DBS on swallowing function in patients with Parkinson's disease, with publication in reference 20) but with a longer follow-up period (at least 6 months) in more patients and a full evaluation in each visit of maximum 2 visits in some patients.

Hypothesis:

The 60Hz stimulation would have persistent benefit in reducing the aspiration, FOG, other axial and motor symptoms in PD patients with bilateral STN DBS and medication refractory FOG at 130Hz stimulation over an extended period of at least months, even corrected for the potential carry-over effects between different test conditions.

Innovation:

This would be the first study on the chronic effect of the 60Hz stimulation on the dysphagia, FOG and other axial and motor symptoms in PD with bilateral STN DBS with medication refractory FOG at 130Hz stimulation.

Significance:

This study will provide a high evidence level and clinical recommendation on the chronic effect of the 60Hz stimulation on the treatment of the axial symptoms, particularly dysphagia and FOG, which are refractory to usual DBS setting and medications and associated with high morbidity and mortality in PD.

Aims:

Aim 1a: A study on the chronic effect (at least 6 months) of 60Hz stimulation on axial symptoms, including swallowing function and FOG, and parkinsonism to see whether the beneficial effect of 60Hz stimulation compared to 130Hz as revealed in our previous study²⁰, could be sustained in PD patients with bilateral STN DBS with medication refractory FOG at 130Hz.

Aim 1b: This study would also clarify the potential carry-over effect on stimulation (DBS 60Hz, DBS 130Hz, and DBS off, 30 min apart) on acute and chronic phase of the study to

enhance the quality of the study, and the level of evidence and recommendation in clinical applications.

Approach:

Towards that aim, we will add 12 patients with medication refractory FOG at 130Hz of bilateral STN stimulation at medication on state for two visits of at least 6-months apart. We will plan to have 14 patients enrolled for visit 1, as 2 of them might drop off (or being unable to be on 60Hz due to worsening tremor) before visit 2 (estimated based on our previous study that 1 out of 7 patients could not be on 60Hz due to worsening tremor²⁰). The previous 6 study patients remaining on 60Hz stimulation after the completion of our previous study will be assessed again at visit 2 at least 12 months after the initial visit 1 once we get the IRB approval here.

We will then combine the data from these 14 newly added patients with the previous 7 patients at visit 1 to make 21 patients to complete the visit 1, and 18-20 (12 to 14 newly added patients plus previous 6) patients to complete a longer interval visit 2 of at least 6 months apart.

As our previous study²⁰, it will still be a randomized double-blind prospective cross-over study with medication on state but with 6-8 patients on each group of starting condition (60Hz vs 130Hz vs DBS off, 30 min apart) to allow us analyze the chronic effect and potential carry-over effect of stimulation between different conditions to increase the level of evidence, with 80% power to detect at least 25% difference at two-tail α level of 0.05, as estimated before²⁰. Aspiration frequency on MBS, difficulty in swallowing on questionnaire, FOG in SWS test and questionnaire, and axial subscore and UPDRS-III score will all be assessed accordingly under each DBS conditions as we did in our previous study²⁰, at both visit 1 and visit 2 of at least 6 months apart. The study will be finished in 2 years.

Specifically, all the study patients will sign a written consent after the IEB approval. The study will be conducted at the Parkinson's Disease and Movement Disorder Center of Department of Neurology, Department of Radiology, Speech and Swallowing Section of Department of Surgery, and Center for Research Informatics at the University of Chicago from August 15, 2015 to March 15, 2017. Advanced PD patients with bilateral STN DBS placement and medication-refractory FOG at routinely used 130-Hz stimulation will be enrolled. The demographics of patients, such as gender, age at the study, disease duration, duration on bilateral STN DBS, and their Parkinson medications, electrode position and active contact positions and settings will all be recorded.

During visit, each patient will receive 3 routine modified barium swallow (MBS) studies in a single day under 3 different DBS frequency conditions (bilateral DBS 130 Hz, DBS 60 Hz, or DBS off) with their usual DBS voltage, pulse width, contact setting, and parkinsonian medication-on state regardless of the study stimulation frequency used. The study will be performed in a randomized and double-blind manner. The order of the DBS conditions will be assigned by the neurologist who will randomly pick up one of the 3 folded sheets with different conditions written on them and program the DBS accordingly, but will not be allowed to participate in any rating or evaluation. Neither the patients, nor the clinical rater, the pathologists for speech and swallowing, or the radiologist is aware of the DBS stimulation frequency condition. A single certified rater will rate all of the clinical scales and questionnaires, and a single swallowing team will conduct all MBS studies and the Penetration-

Aspiration Scale ratings²⁵ to ensure consistency and quality of the evaluation. The MBS protocol consists of a standardized videofluorographic recording of oropharyngeal swallow in lateral and anterior-posterior views, and the anterior-posterior views. The subjects will be given radiopaque liquid, pureed contrast material, and solids coated in barium paste. The examinations will be recorded on the TIMS-DICOM digital medical recording system at high resolution of 30 frames per second. Frame-by-frame analysis will be used to evaluate oral, pharyngeal, laryngeal, and cricopharyngeal function. For the purposes of this study, special attention will be given to aspiration. Laryngeal penetration and aspiration events will be assessed using the Penetration-Aspiration Scale. The frequency of aspiration events will be calculated by adding the number of swallows within each DBS condition that generates a Penetration-Aspiration Scale. The swallowing questionnaire will be completed by each patient after the MBS study under each DBS condition²⁶. The parkinsonian motor, axial, and tremor symptoms as reflected by the Unified Parkinson's Disease Rating Scale, Part III (UPDRS-III) score, axial subscore (including gait, stance, posture, postural stability, and speech), and tremor subscore, respectively, and the FOG as reflected by a FOG questionnaire score,²⁷ and stand-walk-sit (SWS) test on FOG spell times and the time needed to finish the test (seconds) will also be assessed before the MBS study under each DBS condition. The patients will be on each DBS condition for at least 30 minutes before the study. The subjects will be video recorded while walking. The DBS condition producing the best gait function (least FOG, which was 60 Hz for all of our previous patients) will be continued for at least 6 months for the newly enrolled patients.

Analysis: Changes in measurements between the 60Hz and 130Hz will be analyzed using paired t-test, with swallowing function (objective MBS study and subjective swallowing questionnaire) and FOG (objective SWS study and subjective questionnaire) as primary outcomes, and the rest (UPDRS-III score, axial subscore and tremor subscore) as the secondary outcomes in both acute visit1 and chronic visit 2 phase. Changes between other clinically relevant DBS conditions, including 60Hz vs DBS off, 130Hz vs DBS off, and 60Hz vs 60Hz follow-up (for >8 months on average) will also be explored and similarly analyzed with Bonferroni correction. A two-tailed alpha level of 0.05 will be taken as statistically significant for the comparisons.

Foreseeable difficulty or complications:

We don't anticipate any difficulty in conducting this study, as we had a successful similar study before²⁰, with IRB approval (University of Chicago). Medication refractory tremor could offset the 60Hz use as the tremor could be worse compared to 130Hz. However, most of the patient with axial symptoms has less tremor, and medication refractory tremor is even less. In the past, we had only 1 out of 7 patients who could not be on 60Hz stimulation due to the worsening of the tremor²⁰. No complication of aspiration pneumonia was found or reported before. The DBS condition used in the study will be the routine range of condition used in daily living without side effects. There is no alternative ways to conduct current study in order to get the important questions answered.

Pregnant woman, children or mentally retarded patients: None of them will be involved, as these advanced patients are all at the post-menopausal age. No children will be involved in

these advanced PD patient population. No mental retarded patient will be involved. All the patients will have the capacity to consent.

All study subjects will be paid \$200 for their participation in each visit study.

Research Environments:

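### The pooled visit-1 comparison of 60Hz with 130Hz is not independent of the earlier publication: 7 of its 21 patients were already reported, and no result by cohort is planned

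*Combined protocol and SAP*

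**What the plan says.** The text before the Hypothesis heading states: "This study is basically an extension study of our previous one", and identifies that study as one "with publication in reference 20". The Approach section sets the visit-1 set: "We will then combine the data from these 14 newly added patients with the previous 7 patients at visit 1 to make 21 patients". It has the earlier patients return only for visit 2, so their visit-1 values can only be the data already collected.

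The direction of those data is on record. The background says that 60Hz, compared with 130Hz, "decreased not only the aspiration frequency by modified barium swallowing (MBS) test and swallowing difficulty by swallowing questionnaire, but also the medication refractory FOG". The Approach section says that the condition with the best gait was the one with "least FOG, which was 60 Hz for all of our previous patients".

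The Analysis section states: "Changes in measurements between the 60Hz and 130Hz will be analyzed using paired t-test". Swallowing function and FOG are primary. The three remaining scores are listed "as the secondary outcomes in both acute visit1 and chronic visit 2 phase"; I read the two visits as applying to the primary outcomes too, because the Approach section has all outcomes assessed at both. The supplied text contains no cohort term, no comparison of cohorts and no result for the 14 new patients alone.

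Aim 1a asks "whether the beneficial effect of 60Hz stimulation compared to 130Hz as revealed in our previous study" can be sustained, so persistence is the main question.

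**The concern.** A p-value from 21 patients looks like a fresh result, but a third of these patients had been analysed, published and found to favour 60Hz before the plan was written. The pooled test starts with that advantage, and the plan as written would not show whether the 14 new patients point the same way.

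The study is meant to raise the level of evidence and of clinical recommendation. A reader or meta-analyst who takes the visit-1 result together with the earlier publication would count the same 7 patients twice.

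**Working it through.** **Inputs from the documents.** 14 new and 7 earlier patients (Approach); paired t-test, two-tailed alpha 0.05 (Analysis); earlier direction in favour of 60Hz (background, Approach). **Not in the documents:** the earlier p-value, the effect size and the SD of the paired difference. All of these are assumed below.

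**1. The plan's own figure.** 14 + 7 = 21, as stated. The share already known is 7/21 = 33%; the new share is 14/21 = 67%. The stated 80% power for a 25% difference cannot be reproduced without an SD.

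**2. False-positive rate of the pooled test with no true effect.** Normal paired differences were simulated for 7 + 14 patients (4,000,000 runs), with a pooled two-sided t-test on 20 degrees of freedom at 0.05.

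| What is known of the earlier 7 | Pooled test rejects | New 14 alone reject |
|---|---|---|
| Nothing | 5.0% | 5.0% |
| Mean favours 60Hz (documented) | 5.0%, of which 4.8% in favour of 60Hz | 5.0% |
| p<0.10 in favour of 60Hz (assumed) | about 16% | 5.0% |
| p<0.05 in favour of 60Hz (assumed) | about 19% | 5.0% |

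Unconditionally, rejections in favour of 60Hz would be 2.5%. The documented direction alone therefore moves errors to the 60Hz side without changing the two-sided total.

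**3. Hand check by normal approximation.** Z21 = √(7/21)·Z7 + √(14/21)·Z14. If the earlier p was exactly 0.05, Z7 = 1.96, and pooled significance needs Z14 > (1.96 − 0.577 × 1.96)/0.816 = 1.015. With no effect in the new patients, that has probability 0.155. The simulated t-test version gives 0.197. Both are well above 0.05.

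**4. What the new patients would have to show (assumed earlier p = 0.05, sample SD 1 in each cohort).**
- Earlier mean = 2.447/√7 = 0.925 SD. Take a new-14 mean of 0.240 SD.
- Pooled mean = (7 × 0.925 + 14 × 0.240)/21 = 0.468.
- Pooled sum of squares = 6 + 13 + (7 × 14/21) × (0.925 − 0.240)² = 21.19, so the pooled SD is √(21.19/20) = 1.029.
- t = 0.468 × √21/1.029 = 2.09, which is the critical value on 20 degrees of freedom (2.086).
- The new 14 alone give t = 0.240 × √14 = 0.90 on 13 degrees of freedom, p = 0.385.

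So the pooled test could reach p = 0.05 while the new patients show a small and imprecise difference.

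**5. Precision of the new 14.** The 95% confidence half-width is t/√n: 2.160/√14 = 0.58 SD, against 2.086/√21 = 0.46 SD for all 21. If 80% power is assigned to n = 21, the standardised paired effect is 0.643 SD (back-solved, not documented); for that effect 14 patients have 60% power.

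**The case against.** The pooling is open, and the study calls itself an extension. It does not promise a replication of the acute effect. The main hypothesis is persistence, and visit-2 measurements are new for everyone. All of that stands. The unconditional error rate is 5%, and the inflated rates depend on an earlier p-value that the documents do not give. That stands too, so these rates illustrate a range and do not measure the problem in this plan.

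Three stronger readings are tempting and are not supported.

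- *The visit-1 result is no new evidence.* Two thirds of the patients are new. Only the independence of the pooled p-value from the publication is limited.
- *The plan contradicts itself.* It does not: the pooled set is stated, the earlier study is named, and no confirmation by new data is claimed.
- *Pooled significance would often hide a failure in the new patients.* Given an earlier mean favouring 60Hz, the new 14 alone are not significant in 59% of the pooled results significant for 60Hz with no true effect, and in 28% with an assumed effect of 0.64 SD. Without conditioning on the earlier result, the figures are 56% and 27%. Nearly all of this is the smaller sample, so it does not measure the effect of pooling.

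A separate set of significance tests in 14 patients would also add tests at reduced power and invite misreading. For that reason the fix asks for estimates and intervals.

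What remains is that visit 1 is tested on primary outcomes, the study is presented as raising the level of evidence, and nothing in the plan lets a reader separate new data from old.

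**Conclusion.** The point holds as a limit on how the visit-1 result can be read. The pooled p-value shares 7 of its 21 patients with a publication whose direction was known, so it is a cumulative result and not independent of that publication. It does not make pooling wrong, and it does not touch the persistence question at visit 2.

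The size is conditional: 5% with no conditioning, about 16% or 19% if the earlier 7 had p<0.10 or p<0.05 in favour of 60Hz. These rates assume normal paired differences with the same variance in both cohorts and no true effect in either. A reader might infer that the trial's error rate is 19%; the documents do not support that, because they report the earlier direction only. The absence of a cohort-specific result is judged on the supplied text. Label: cheap improvement.

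**What to change.** Add to the Analysis section:

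> At visit 1, the paired 60Hz vs 130Hz mean difference and 95% confidence interval for each primary outcome will be reported for the 14 newly enrolled patients beside the earlier 7. The pooled 21 is the overall estimate and will be labelled cumulative, including patients already reported. Any statement that new data support the acute effect will rest on the 14 new patients.

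This needs analysis text only: no new data, no change to the visits, and no loss of power for the pooled estimate. The cost is that the new-14 estimate is less precise (step 5 of the working). A confidence interval that includes zero in the 14 must therefore not be read as absence of effect, and the report should say so.

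### The visit 2 sample size rests on 6 earlier patients still on 60Hz where the background says 5, and the carry-over aim has no planned analysis

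*Combined protocol and SAP*

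**What the plan says.** **Patient count.** The Approach section enrols 14 new patients and expects at least 12 at visit 2, because "2 of them might drop off (or being unable to be on 60Hz due to worsening tremor) before visit 2". The basis is "estimated based on our previous study that 1 out of 7 patients could not be on 60Hz due to worsening tremor". To these it adds earlier patients: "The previous 6 study patients remaining on 60Hz stimulation after the completion of our previous study will be assessed again at visit 2". The total is "18-20 (12 to 14 newly added patients plus previous 6) patients to complete a longer interval visit 2".

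The background, before the Hypothesis heading, gives another count: "all of our 5 out of 7 patients who was on 60Hz simulation for 6-week study period remains on 60Hz since then". It continues: "The 2 of the 7 patients were not on 60Hz stimulation after the previous study". The reasons are slightly worse tremor in one patient and "skin infection after the battery replacement (unrelated to the study) in another one". Earlier in the background only the tremor case appears: "one of the patients had to switch back to 130Hz stimulation in 3 weeks due to worsening of the hand tremor". The section on foreseeable difficulties also counts that one patient only.

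**Carry-over.** Aim 1b is to clarify carry-over between the three conditions, given 30 minutes apart, in both the acute and the chronic phase. The hypothesis says that the 60Hz benefit will hold after correction for carry-over. The Approach section gives the analysis of the chronic effect and of carry-over as the reason for its starting-condition groups. In the same sentence it states 80% power for a 25% difference, by reference to the earlier study. The Analysis section plans paired t-tests of 60Hz against 130Hz at each visit, and similar paired comparisons, Bonferroni-corrected, for other pairs. It has no period, order or carry-over term.

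**The concern.** The Approach and the background describe the same seven patients after the same study and differ by one. Visit 2 is where Aim 1a, the chronic effect, is answered, so its size should follow from counts that agree.

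The carry-over gap matters more. Carry-over is an aim and part of the hypothesis, yet no planned analysis estimates it or removes it from the 60Hz-130Hz difference. The method could then be chosen after the data are seen, or a non-significant comparison in small groups could be reported as evidence that there is no carry-over. The trial could follow its Analysis section exactly and still leave Aim 1b unanswered.

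**Working it through.** **1. The plan's own total.** Inputs from the Approach section: 14 new patients, 2 possible losses, 6 earlier patients.
- Loss allowance: 14 × 1/7 = 2, leaving 12.
- Visit 1: 14 + 7 = 21.
- Visit 2: 12 + 6 = 18 to 14 + 6 = 20. The stated 18-20 is reproduced.

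**2. Where the 6 comes from.** Removing only the tremor patient gives 7 − 1 = 6. Removing both patients named in the background gives 7 − 2 = 5. Visit 2 is then 12 + 5 = 17 to 14 + 5 = 19.

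**3. What one patient costs.** The plan gives no SD, endpoint, test or n for its 80%, so the reference n is an assumption here. For a paired t-test (noncentral t, two-sided 0.05), 80% power needs a mean difference of 0.701 SD of the paired differences at n=18. Keeping 0.701 and taking n=17 gives power of 77%. If the 80% was set at n=20 (0.660 SD), n=17 gives 72%. If it was set at n=7 (1.273 SD), n=17 gives 99.8%.

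**4. Whether the paired t-test handles carry-over.** Take the six possible orders of three conditions, used equally often. Let λ be the effect that a condition leaves on the next measurement, and assume none in the first period.
- 60Hz comes first in 2 of 6 orders, after 130Hz in 2 and after DBS off in 2. Its mean contains (λ130 + λoff)/3.
- 130Hz comes first in 2 of 6, after 60Hz in 2 and after DBS off in 2. Its mean contains (λ60 + λoff)/3.
- The mean paired difference, 60Hz minus 130Hz, therefore equals the true difference plus (λ130 − λ60)/3.

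Even with perfect balance, one third of the carry-over contrast stays in the estimate. The paired test neither shows it nor removes it.

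**5. What a crossover model can deliver.** Assume 18 patients, 3 on each order, one visit, a normal outcome with equal SD in each period and within-patient correlation ρ. Fit condition, period, preceding condition and a fixed effect for each patient.
- Residual df = 54 − 18 − 2 − 2 − 2 = 30, so t = 2.042.
- The variance of a pairwise carry-over contrast is (4.5/18)(1 − ρ)SD², so its SE is 0.5 × √(1 − ρ) SD.
- 95% half-width = 2.042 × 0.5 × √(1 − ρ): 1.02 SD at ρ = 0, 0.72 at 0.5, 0.56 at 0.7. Random patient effects give 0.91, 0.70 and 0.55.
- The adjusted 60Hz-130Hz difference has variance (2.5/18)(1 − ρ)SD², against (2/18)(1 − ρ)SD² unadjusted. The ratio is 1.25, so the SE rises by about 12% (√1.25 = 1.118).

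**The case against.** **The counts may refer to different dates.** One patient left 60Hz during the 6-week study, so 6 could be the number at its completion, and 5 the number after follow-up of up to 14 months. The infection patient might also return for visit 2. This is possible, but the background says that both patients were off 60Hz after the previous study, and the Approach defines its 6 as still on 60Hz after that study. The texts still need reconciling. It stands that the gap is one patient and that 17-19 overlaps 18-20.

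**Stronger readings that the documents do not support.**
- *The 80% power is wrong.* It is referred to the earlier study, whose inputs are not in these documents. It cannot be checked, but nothing shows it to be in error.
- *With 17 patients the starting groups of 6-8 fail.* No split of 17 puts 6 in each of three groups, but the Approach does not tie 6-8 to visit 2. At visit 1, 21/3 = 7 sits in the middle of that range.
- *The loss rate should be 2/7.* The second patient stopped for an infection that the plan calls unrelated to the study, and being off 60Hz is not the same as missing visit 2.
- *The 60Hz-130Hz comparison is invalid.* The paired analysis remains usable. It does not deliver the promised correction.

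**The Approach does mention analysing carry-over.** It states the intention and supplies randomised starting conditions, but names no method. Comparing starting groups alone would be a weak substitute: the third period follows the second condition, not the starting one, and a two-group comparison with 5 to 7 per group has a half-width of about 1.5 to 1.2 SD.

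**Conclusion.** Two points hold on the text. First, the Approach and the background disagree on how many earlier patients remain on 60Hz. The documents do not settle which count is right. If it is 5, visit 2 is 17-19 instead of 18-20, a small change (power of about 77% at n=17 if 80% was set for a paired test at n=18). Second, Aim 1b and the correction promised in the hypothesis have no analysis. This is the more consequential point and depends on no assumed figure. Only the precision figures do: they rest on 18 patients, balanced orders, no carry-over into the first period and an assumed correlation of 0 to 0.7.

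Because the power sentence follows directly on the mention of carry-over, a reader might infer that 80% applies to it. The plan gives no derivation for that, and the figure should not be read so. This should be fixed before the data are analysed. It does not undermine the main paired comparison.

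**What to change.** 1. Reconcile the count of earlier patients between the background and the Approach. If it is 5, restate visit 2 as 17-19.
2. Add to the Analysis section, for each primary measure at each visit, a within-patient crossover model with terms for condition, period and preceding condition, using the randomised order already assigned. State how the first period is coded, since no test condition precedes it.
3. Report the carry-over contrasts and the carry-over-adjusted 60Hz-130Hz difference with 95% confidence intervals, beside the paired t-test. State that absence of carry-over will not be inferred from a non-significant result.
4. Word the 80% power statement so that it does not extend to carry-over.

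The cost is one added analysis and possibly a slightly smaller stated size, with no extra patients or visits. The adjusted difference will be somewhat less precise than the paired one. With half-widths of about 0.55 to 1.0 SD, wider if the orders turn out unbalanced, the plan must accept that Aim 1b may yield an estimate without a firm answer.

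### The 80% power for a 25% difference is also claimed for carry-over without support, and on the SD implied by the planned paired test, starting groups of 6-8 fall short of it

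*Combined protocol and SAP*

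**What the plan says.** The document is the combined protocol and SAP. In the Approach section, one sentence carries the whole sample-size argument. It plans "6-8 patients on each group of starting condition" (60Hz, 130Hz or DBS off), so as to analyse both the chronic effect and the "potential carry-over effect of stimulation between different conditions to increase the level of evidence, with 80% power to detect at least 25% difference". The sentence continues "at two-tail α level of 0.05, as estimated before", citing the earlier study. The same section gives that study 7 patients and expects 21 patients at visit 1 and 18-20 at visit 2.

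Carry-over is a stated aim. Aim 1b reads: "This study would also clarify the potential carry-over effect on stimulation". The Hypothesis also expects the 60Hz benefit to remain after correction for carry-over.

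The Analysis section names a paired t-test for 60Hz vs 130Hz and similar Bonferroni-corrected tests for other pairs of conditions. It lists no carry-over, period or sequence analysis.

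**The concern.** The sentence gives one power figure to two comparisons of very different precision. The 60Hz vs 130Hz contrast is made within each of 18-21 patients. Carry-over judged by starting condition is a contrast between groups of 6-8 patients. At a common SD the second is much weaker, so a figure derived for the first does not transfer to the second.

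Aim 1b is at stake. Conditions are only 30 minutes apart, and the 60Hz claim leans on carry-over having been examined. If the protocol states 80% power for carry-over and the real power is lower, a non-significant result carries less reassurance than the stated figure suggests.

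**Working it through.** **Inputs.** From the Approach section: two-sided alpha 0.05, power 80%, difference 25%, 6-8 patients per starting condition, 21 patients at visit 1, 18-20 at visit 2, 7 in the earlier study. From the Analysis section: paired t-test for 60Hz vs 130Hz. The SD, the endpoint and the scale of the 25% are not given. SDs below are therefore assumptions, in the same percentage units as the 25%.

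**1. The plan's own figure.** It cannot be reproduced without an SD. The SD can only be solved for, by assuming that 80% is exact for the paired test. Power is taken from the noncentral t distribution with n-1 df and noncentrality d√n, where d = 25/SD.

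- n=7: d = 1.273, so SD of differences = 25/1.273 = 19.6%.
- n=18: d = 0.701, so SD = 25/0.701 = 35.7%.
- n=21: d = 0.643, so SD = 25/0.643 = 38.9%.

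**2. The same difference compared between two starting groups of m.** Noncentrality is d√(m/2), with 2m-2 df. For m=6 and SD 19.6% it is 1.273 × √3 = 2.20 with 10 df, giving 51%. For m=6 and SD 35.7% it is 0.701 × √3 = 1.21, giving 20%.

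| SD of differences | m=6 | m=7 | m=8 |
|---|---|---|---|
| 19.6% (80% exact at 7 pairs) | 51% | 59% | 66% |
| 35.7% (80% exact at 18 pairs) | 20% | 23% | 26% |
| 38.9% (80% exact at 21 pairs) | 17% | 20% | 22% |

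**3. The SD at which the claim would hold.** For 80% power the two-group test needs d = 1.796, 1.632 or 1.507 at m = 6, 7 or 8. The largest SD allowed is then 25/1.796 = 13.9%, 25/1.632 = 15.3% or 25/1.507 = 16.6%.

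**4. A more efficient analysis.** Take a model with patient, period, current condition and preceding condition, and all six orders used equally. Here carry-over means the contrast between two preceding conditions, which is not the same quantity as in step 2. At n=18 its variance is 0.250σ², where σ = SD of differences/√2, with 54-18-6 = 30 df.

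- SD 19.6%: σ = 13.9, standard error = 0.5 × 13.9 = 6.95, ratio 25/6.95 = 3.60, power 94%.
- SD 35.7%: σ = 25.2, standard error = 12.6, ratio 1.98, power 48%.

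At n=21 the six orders cannot be filled equally, so power depends on which orders get the extra patients and on the contrast: about 95-97% at SD 19.6% and 52-58% at SD 35.7%.

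**5. Whether 6-8 per group is assured.** The order is drawn from three folded sheets, with no balancing described. If 21 starting conditions were independent draws with probability 1/3 each (an assumption), the chance that all three groups fall within 6-8 is about 24%: 0.038 for 7/7/7 plus 0.200 for the arrangements of 6/7/8.

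**The case against.** The strongest reply is that nothing here proves the claim false. The SD is unknown, and its basis lies in a cited publication outside the documents. The sponsor could hold an SD below about 14-17%, and then 6-8 per starting group would reach 80% while the paired test at n=18 would exceed 99%. The wording is also a floor, not an exact value: a figure derived for 7 patients and kept for a larger sample would be conservative for 60Hz vs 130Hz. An efficient within-patient model could reach 94% or more at SD 19.6%.

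Much of this stands. A reader might infer that groups of 6-8 cannot give 80% power whatever the SD. The documents do not support that. A reader might also infer that carry-over power is a quarter or less. That describes only the starting-group test at the larger SDs.

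It does not rescue the sentence as written. The documents offer no evidence for so small an SD. They link the figure to a 7-patient study in which, by the protocol's own background, carry-over was left unresolved. The efficient model and the balanced orders it needs are not in the plan.

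**Conclusion.** The 80%/25% figure is unsupported for carry-over. If it describes the planned paired test, it is not met by a comparison of starting groups of 6-8: power is 51-66% on the 7-pair basis and 17-26% on the 18-21-pair basis. These values assume that 80% is exact for the paired test, that the same SD applies in each group, and that carry-over is judged by comparing the 60Hz-130Hz difference between two starting groups. A within-patient model narrows or closes the gap, depending on the SD.

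A reader might infer that the investigators will treat a non-significant test as proof of no carry-over. The plan does not say so; it speaks of correcting for carry-over and gives no test or decision rule. The more basic gap is that Aim 1b has no specified analysis. The point should be addressed before the analysis, but it does not undermine the 60Hz vs 130Hz comparison itself.

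**What to change.** In the Approach section, limit the power statement to the within-patient 60Hz vs 130Hz comparison. Recompute it for the visit-2 number, and state the endpoint, the scale of the 25% and the SD. The visit-2 number needs settling first: the background has 5 earlier patients remaining on 60Hz, while the Approach section counts 6.

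In the Analysis section, add a within-patient model with period and preceding-condition terms for Aim 1b. Report carry-over with its 95% CI, and state that a non-significant result will not be taken as showing no carry-over. Give the carry-over detectable with 80% power under the orders actually used, from the sponsor's own SD. The SDs solved for above only illustrate the problem and should not go into the protocol.

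The cost is a few sentences, a little more analysis and a less favourable stated figure for Aim 1b. No extra patients are needed.
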